9.1 ADVERSE EVENT ASSESSMENT

All adverse events, including the following, will be assessed by the Investigator via interview, and recorded in the subjects study chart and on the appropriate case report form pages.

- Observed or volunteered problems
- Complaints
- Physical signs and symptoms
- Medical condition which emerges during the study, having been absent at baseline
- Medical condition present at baseline, which appears to worsen during the study

The need to capture AEs is not dependent upon whether or not the clinical event is associated with the use of the investigational product.

Each AE must be described as follows: the date of onset, date of resolution, severity, frequency of the event (single episode, intermittent, continuous), action taken (none, medical and/or surgical), relationship to investigational device, and seriousness criteria must be recorded. Each adverse event must be recorded separately.

Severity will be assessed using the following definitions:

Mild	Aware of sign or symptom, but easily tolerated
Moderate	Discomfort enough to cause interference with usual activity
Severe	Incapacitating with inability to work or do usual activity

The relationship to investigational device will be assessed by the Investigator using the following definitions:

Not Related	Evidence exists that the adverse event definitely has a cause other than the investigational device (e.g. pre-existing condition or underlying disease, intercurrent illness, or concomitant medication) and does not meet any other criteria listed.
Possibly Related	A temporal relationship exists between the event onset and administration of investigational device. Although the adverse event may appear unlikely to be related to the investigational device, it cannot be ruled out with certainty; and or the event cannot be readily explained by the subject's clinical state or concomitant therapies.
Probably Related	A temporal relationship exists between the event onset and administration of investigational device, and appears with some degree of certainty to be related based on known therapeutic and pharmacologic actions of the investigational device. It cannot be readily explained by the subject's clinical state or concomitant therapies.
Definitely Related	Strong evidence exists that the investigational device caused the adverse event. There is a temporal relationship between the event onset and administration of the investigational device. There is strong therapeutic and pharmacologic evidence that the event was caused by the investigational device. The subject's clinical state and concomitant therapies have been ruled out as a cause.

9.2 ADVERSE EVENT REPORTING

All subjects who have been exposed to the investigational device will be evaluated at baseline and future visits by a clinician for adverse events via interview. All adverse events will be evaluated beginning with onset, and evaluation will continue until the last day of the study, until resolution or recovery is observed

or until the Investigator determines that the subject's condition is stable, whichever is earlier. The Investigator will take all appropriate and necessary therapeutic measures required for resolution of the adverse event. Any medication necessary for the treatment of an adverse event must be recorded on the concomitant medication case report form.

If more than one distinct adverse event occurs, each event should be recorded separately. The study period during which adverse events must be reported is normally defined as the period from the initiation of any study procedures to the end of the study. For this study, the endpoint is defined as the last administration of study treatment.

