If assessments are done as part of an early discontinuation visit, subject should be asked to come in for the post-treatment follow-up visit.

- Vital Signs
- Weight
- HAM-D/MADRS
- IDS-SR
- C-SSRS
- Adverse Events
- Concomitant Medications
- Treatment Blinding Confirmation Questionnaire(s)
- Determination of eligibility for open label sTMS treatment

Open Label Evaluation Visits (Week 7-12)

In addition to the treatment visits, an evaluation visit will be conducted on the last day of each weekly treatment cycle. The following assessments will be performed as part of that evaluation:

- HAM-D/MADRS
- IDS-SR
- C-SSRS
- Adverse Events
- Concomitant Medications

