8 DISCONTINUATION

8.1 WITHDRAWAL FROM STUDY

Subjects have the right to withdraw from the study at any time, for any reason, without jeopardizing their medical care. The Investigator, the IRB and NeoSync, Inc. also have the right to withdraw subjects or terminate the trial for the following reasons:

- Occurrence of unacceptable risk to the subjects enrolled in the study, including significant worsening of depression.
- A decision on the part of the Sponsor to suspend or discontinue testing, evaluation, or development of the product.

The Investigator may use the weekly clinical evaluation to determine if the subject's symptoms or quality of life have significantly deteriorated to the point where withdrawal from the study would be in the subject's best interests.

A study conducted at a single study site or a single study site in a multicenter study may also warrant termination under the following conditions:

- Failure of the Investigator to comply with pertinent regulations of appropriate regulatory authorities.
- Insufficient adherence to protocol requirements.
- Submission of knowingly false information from the research facility to the Sponsor, study monitor, or appropriate regulatory authority.

Subjects who withdraw from the study for any reason will not be replaced. Subjects who voluntarily withdraw from the study will be asked to complete the Week 6/Early Termination assessments. Subjects who are withdrawn due to adverse events will be followed until resolution or stabilization of the adverse event.

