8.2 REASONS FOR DISCONTINUATION OF SUBJECTS

Subjects may decide to discontinue their participation in the study for various reasons such as unmanageable side effects, lack of efficacy, withdraw of consent, etc. The PI may also decide to withdraw the subject for reasons including: protocol noncompliance, safety concerns, etc.

Sites will attempt to gather information for all subjects that discontinue from the study whenever possible. The sites shall, at minimum, collect details regarding the subject's primary reason for discontinuing, HAM-D, MADRS, current medication use, and adverse events. Other scales may be collected, based upon the subject's availability.

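### Section 9.2 ends adverse event reporting at the final treatment, in conflict with event collection at early termination and with the follow-up rule in Section 8.1

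*Protocol*

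**What the plan says.** **Reporting window.** Protocol Section 9.2 opens the window with the first study procedure: "The study period during which adverse events must be reported is normally defined as the period from the initiation of any study procedures". By default it runs to the end of the study. The next sentence sets a limit specific to this trial: "For this study, the endpoint is defined as the last administration of study treatment". No days are added after that point.

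**Collection after an early stop.** Section 8.1 states: "Subjects who voluntarily withdraw from the study will be asked to complete the Week 6/Early Termination assessments". Section 7.3, the flowchart in Appendix I and the SAP (Follow-up Visits and Table A) all list adverse events among those assessments. Section 7.3 adds: "If assessments are done as part of an early discontinuation visit, subject should be asked to come in for the post-treatment follow-up visit". That further visit is not in the schedule in Section 7.1 or in the flowchart. Section 8.2 sets a minimum data set for everyone who discontinues, to be gathered whenever possible: "The sites shall, at minimum, collect details regarding the subject's primary reason for discontinuing, HAM-D, MADRS, current medication use, and adverse events".

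**Follow-up of known events.** Section 9.2 gives two end points first: "evaluation will continue until the last day of the study, until resolution or recovery is observed". It then adds a third, a judgement of stability, and makes the first of the three decisive: "or until the Investigator determines that the subject's condition is stable, whichever is earlier". Section 8.1 says: "Subjects who are withdrawn due to adverse events will be followed until resolution or stabilization of the adverse event". The SAP repeats the Section 8.1 sentence under Withdrawal and Replacement of Subjects.

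**The concern.** Two stated rules appear to conflict with other stated rules.

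First, the mandatory window closes at a subject's last session, yet the visit meant to record what happened to an early leaver normally takes place later. A site that follows Section 9.2 literally could omit an event that a site following Sections 7.3 and 8.2 would record.

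Second, a known event in a subject withdrawn because of it has two different end points for follow-up.

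Safety is part of the primary objective (Section 2), and Section 11.6 rests the safety assessment mainly on the frequency of recorded adverse events. Up to 16 sites are planned (Synopsis). What is at stake is uniform capture of events in subjects who stop early. Serious events may be affected too, because Section 9.3 requires prompt reporting of those that occur during the study, and the only stated end for adverse event reporting is the one in Section 9.2.

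**Working it through.** The point rests on comparing the text; the plan gives no figure for it to reproduce.

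**1. Where the window and the last visit coincide.** Section 7.1 and Appendix I place the Week 6 evaluation at Treatment Day 30, which is also the day of the last double-blind session. Section 7.3 places each open-label evaluation on the last day of the weekly cycle. So for a subject who completes either phase and then stops, the gap between last treatment and last evaluation is zero, and Section 9.2 does no harm.

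**2. Where they separate.** Let a subject leave the double-blind phase with the last session on day t and the early-termination visit on day t + g.
- Section 9.2 makes reporting mandatory up to day t.
- Sections 7.3 and 8.2 ask for adverse events at day t + g.
- An event that starts after t and by t + g is requested by the second rule and outside the first.
- If the subject also attends the post-treatment follow-up visit, the uncovered stretch is longer.

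The documents give no value for g and no date for the follow-up visit. For a subject who leaves the open-label phase early, neither Section 7.3 nor Appendix I lists a termination visit, so only the minimum data in Section 8.2 apply.

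**3. Follow-up of a known event.** Let L be the last day of the study, r the day of resolution or recovery, and s the day the condition is judged stable.
- Section 9.2: follow-up ends at min(L, r, s).
- Section 8.1 and the SAP, for subjects withdrawn because of an event: follow-up ends on resolution or stabilization, that is min(r, s).

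The two differ whenever L comes before both r and s. This holds whether L is taken per subject or for the whole trial. This conflict comes from the cap in Section 9.2, not from the reporting-window sentence: a window for new events can coexist with longer follow-up of events already reported.

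**4. Link to the analysis.** The SAP (Safety Analysis) defines a double-blind treatment-emergent event by a start bound only. An event after the last session would therefore be counted if a site recorded it, and would be missing if the site stopped at the last treatment.

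**5. Scale.** The SAP (Sample Size) expects about 23% of enrolled subjects to fall outside the per-protocol population: 92 / (1 − 0.23) = 119.5, or 120 enrolled, and 120 − 92 = 28. At the maximum size, 240 − 184 = 56. These are not counts of early leavers. Section 11.1 and the SAP also exclude subjects for missed sessions, long visit intervals, prohibited medication or a missing Week 6 HAM-D, and some of those subjects can finish treatment with no gap. The previous NEST trial does not settle it either: 202 − 135 = 67 of 202 subjects (33%) fell outside the completer set (Section 1.1), but that set also required enough sessions and complete assessments.

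**The case against.** The strongest reply is that events are still prompted elsewhere. Section 8.2 makes adverse events part of the minimum data at discontinuation, and Section 7.3, Appendix I and the SAP list them at early termination. The SAP would count a late event once it was recorded. Section 9.2 says what must be reported; it does not tell sites to discard anything later. All of this stands, and it means that loss requires a site to apply one sentence against several others. But those other passages are the ones that conflict with Section 9.2, so they limit the consequence without removing the inconsistency.

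A second reply is that the endpoint in Section 9.2 could mean the last treatment in the whole trial. That would soften the first conflict, but the period begins with a subject's own procedures, so the per-subject reading is the natural one.

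A third is that Section 8.1 can be read as a special rule for withdrawals beside a general rule in Section 9.2. That is possible, but neither section says so.

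A reader might also infer that early leavers are the subjects most likely to have adverse events, so that harm will be understated. The documents do not show this. Section 13.2 reports that, in the prior NEST study, none of the events considered possibly related led to discontinuation, and that early discontinuation rates did not differ significantly between arms.

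**Conclusion.** The inconsistency is real and minor. Section 9.2, read per subject, closes mandatory reporting before the early-termination visit at which other sections ask for adverse events. It also caps follow-up of known events where Section 8.1 and the SAP set no such cap. The result is that capture after the last session may differ between sites, possibly including serious events under Section 9.3.

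The size cannot be stated. It depends on the number of early leavers and on the interval to their termination visit, and the documents give neither. It would be tempting to say that 28 of 120 subjects have an uncovered period. The documents do not support that, because 28 is the planned shortfall from the per-protocol population for all reasons. Nor do they support saying that events will be lost or that Section 8.1 must prevail; they support only that the passages need to be reconciled.

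The conclusion assumes the per-subject reading of the endpoint and an early-termination visit held after the last session.

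**What to change.** - Amend Section 9.2 so that the AE and SAE reporting period runs at least through the subject's last study visit at which adverse events are already collected (Week 6/Early Termination, or the last open-label visit), and say what that visit is for someone who leaves the open-label phase early.
- State whether the period includes the post-treatment follow-up visit named in Section 7.3, and either put that visit in Section 7.1 and Appendix I or remove the reference.
- Use the same period to define what counts as during the study in Section 9.3, and as the end bound of the treatment-emergent definitions in the SAP.
- Reconcile the follow-up rules in Sections 8.1 and 9.2, and carry the result into the SAP. Which rule applies is for the sponsor to decide.

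The core change is one sentence in Section 9.2, with short matching edits elsewhere. Aligning the window with visits that already collect adverse events adds no visit; a longer window would be a separate decision for the sponsor.

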9.3 REPORTING OF SERIOUS ADVERSE EVENTS AND UNANTICIPATED ADVERSE DEVICE EFFECTS

All Serious Adverse Events (SAE) and Unanticipated Adverse Device Effects that occur during the study, including death, must be reported within one working day by telephone to the study's Medical Monitor, and followed up in writing within 24 hours. The urgency for reporting SAE is four-fold: (1) to facilitate discussion (and implementation, if necessary) by the Sponsor and the Investigator of appropriate follow-up measures; (2) to facilitate Investigator reporting of unanticipated problems involving risk to human subjects to the IRB; (3) to facilitate the Sponsor's rapid dissemination of information regarding AEs to other Investigators/sites in a multi-center study; and (4) to enable the Sponsor to fulfill the reporting requirements to the appropriate regulatory authority. Serious adverse events should be reported by phone and facsimile to NeoSync, Inc.

Within the following 48 hours, the Investigator must provide further information on the serious adverse event or the unanticipated problem in the form of a written narrative. This should include a copy of the completed Serious Adverse Event form, and any other diagnostic information that will assist the understanding of the event. Significant new information on ongoing serious adverse events should be provided promptly to the study Sponsor.

10 STUDY OUTCOMES

10.1 PRIMARY EFFICACY OUTCOME

The primary endpoint will be clinical response, defined by 50% or greater reduction on the HAM-D₁₇ total symptom scores following 6 weeks of treatment.

10.2 SECONDARY OUTCOMES

Additional outcomes will include the following:

- The change in symptom scores on the HAM-D₁₇ through 6 weeks of treatment
- The change in symptom scores on the MADRS through 6 weeks of treatment.
- Clinical response, defined by 50% or greater reduction on the MADRS total symptom scores following 6 weeks of treatment.
- Effectiveness of blinding questionnaire

10.3 SAFETY DATA

Safety will be assessed by the following:

- The incidence and severity of all adverse events (including, but not limited to, serious adverse events and no-related adverse events)
- Changes in C-SSRS through 6 weeks of treatment.

11 STATISTICAL METHODS

11.1 POPULATION FOR ANALYSIS

The Intent-to-Treat (ITT) Population will consist of all subjects who are randomized to a study group.

The Per-Protocol (PP) Population is comprised of subjects who receive treatments according to the recommended protocol schedule without any major protocol violation. Major protocol violations include but are not limited to:

- Receiving treatments other than those specified in the study protocol.
- Treatments not administered according to study protocol.
 - Subjects cannot miss more than 1 dose in a treatment week and their weekly visit interval cannot exceed 10 calendar days. Any subject who misses more than 6 doses in the 6 week treatment period (maximum of 60 days) is not considered compliant with the treatment and will not be included in the analysis.
- Receiving concomitant medications that are not allowed per the study protocol.
- HAM-D₁₇ not available at Week 6.

The PP population analysis will serve as the primary analysis population.

The Safety Population will consist of all subjects who received at least one study treatment.

For the six-week open label phase, all efficacy and safety summaries will be based on the combined sTMS-treated subject population, which consists of all subjects who have entered the six-week open label phase. For the open-label phase, all efficacy analyses will be performed on the Observed Cases (OC) dataset only. That is, no imputation for missing data will be used, and only data observed during the follow-up phase will be summarized.

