- Submission of knowingly false information from the research facility to the Sponsor, study monitor, or appropriate regulatory authority.

Subjects who withdraw from the study for any reason will not be replaced. Subjects who voluntarily withdraw from the study will be asked to complete the Week 6/Early Termination assessments. Subjects who are withdrawn due to adverse events will be followed until resolution or stabilization of the adverse event.

SAMPLE SIZE

The primary endpoint of the study is clinical response at Week 6, defined by 50% or greater reduction on the Hamilton Rating Scale for Depression (HAM-D¹⁷) from baseline (Day 0). The null and alternative hypotheses of interest are:

$$H_0: \pi_A - \pi_S = 0$$

vs.

$$H_a: \pi_A - \pi_S \neq 0$$

where π_A is the proportion of subjects who show 50% or greater improvement in HAM-D¹⁷ total score from baseline (Day 0) to Week 6 for the active sTMS treatment and π_S is the equivalent value for the sham-controlled group.

The calculation of sample size requirements for this confirmatory study is based on the results observed in the per-protocol (PP) analysis of non-treatment-naïve subjects who completed Week

6 HAM-D¹⁷ assessments in the previous NEST trial NND-3001.

In that population, 34% of subjects treated with active sTMS were categorized as responders, whereas only 8% of sham treated subjects responded. Assuming true population response rates of 34% for sTMS and 8% for Sham, power analysis indicates that a PP sample size of 92 subjects (i.e., 92 subjects, or 46 subjects per treatment group, without major protocol violations and with HAM-D¹⁷ measured at Week 6) yields 81% power to demonstrate superiority of sTMS over Sham, where the statistical test is Fisher's exact test at a two-sided 0.05 level of significance.

The sample size ratio for the active treatment group to sham-controlled group is 1:1. Based on a conservative estimate of published studies, approximately 23% of enrolled subjects may not be part of the PP population in each treatment group. Thus, a total of 120 subjects (60 per group) will therefore be enrolled in the study to account for potential drop-outs and protocol noncompliance prior to Week 6.

SCHEDULE OF VISITS

Table A on the following page displays the schedule of visits and procedures for protocol NND-3002. Full details can be found in the protocol.

TABLE A: STUDY FLOWCHART

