For the six-week double-blind phase, imputation of data on the primary endpoint will be performed as described below. For the six-week follow-up open-label phase (Weeks 6 – 12), all efficacy and safety summaries will be based on the all sTMS treated subject population, which consists of all subjects who have entered the six-week follow-up Phase. All efficacy analyses will be performed on the Observed Cases (OC) dataset only for each week in this open-label Phase. That is, no imputation will be used, and only data observed during the follow-up Phase will be summarized. Analyses in the open-label phase will be presented by double-blind

treatment group and for both treatment groups combined. Baseline for the double-blind phase will be defined as the last available value measured post-washout and prior to the first double-blind dosing. Baseline for the open-label phase will be defined as (a) the last post-washout assessment measured prior to the beginning of the double-blind treatment phase for patients randomized to sTMS in the double-blind phase; and (b) the last double-blind assessment measured prior to the beginning of the open-label phase for patients randomized to Sham in the double-blind phase.

Analysis of Primary Efficacy Endpoint

HAM-D/MDRS will be assessed at screening, baseline, Week 1-6 Evaluation Visits, and during the open-label phase through Week 12 evaluation visit. The primary efficacy endpoint is clinical response, defined by 50% or greater reduction on the HAM-D¹⁷ from baseline to Week 6. The efficacy analyses will be performed on the PP, ITT with available data, and ITT with imputed data (see below for imputation methods) analysis populations. The PP analysis population is the primary analysis population for efficacy per e-mail discussion between NeoSync and the FDA on July 17, 2015.

The null hypothesis is that the active sTMS treatment group does not differ from the sham group with respect to the proportion of patients with clinical response at Week 6. The corresponding alternative hypothesis is that the active sTMS treatment group differs from the sham group with respect to the proportion of patients with clinical response at Week 6.

Specifically, the primary efficacy analysis will be a test of the hypotheses:

$$H_0: \pi_A - \pi_S = 0$$

and

$$H_a: \pi_A - \pi_S \neq 0$$

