where π_A is the proportion of subjects who show 50% or greater improvement in mean HAM-D¹⁷ total score from baseline (Day 0) to Week 6 for the active treatment and π_S is the equivalent value for the sham-controlled group. The test of the null hypothesis will be based on Fisher's exact test at a two-sided 0.05 level of significance. In addition, the observed response rates and two-sided 95% confidence intervals of the risk difference between treatments will be presented, calculated using the Wilson method discussed in Newcombe (1998).

An assessment of treatment-by-investigative center interaction on the proportion of clinical responders at Week 6 will be carried out using the Breslow-Day test. Sites with fewer than 10 subjects in the PP group will be pooled with other centers by geographic region prior to carrying out analyses (the same pooled sites will then be used for the analyses on the ITT analysis population). The pooling will be carried out before the blind is broken. A 0.15 level of significance will be used to assess the interaction. A non-significant interaction or an interaction significant but only quantitative in nature will support the pooling of results across study centers for the final analysis.

For the six-week open-label follow-up phase, the proportion of patients with a clinical response at each open-label visit for each double-blind treatment and for both treatments combined will be presented. The proportion of patients with a clinical response at each visit will be compared between double-blind treatment in a similar manner as above. These open-label analyses are

considered exploratory.

INTERIM ANALYSES

Due to uncertainty regarding the expected sham response rate and resulting treatment effect differential, this study will utilize an adaptive design that allows one interim sample size re-estimation after a minimum of 70 subjects have been enrolled and completed 6 weeks of treatment (or dropped out prior to 6 weeks). The pre-specified maximum allowable adjusted sample size following re-estimation will be 240 randomized, or two times the initial planned sample size of 120 enrolled, based on practical resource constraints and the desire to achieve a minimum differential of 12% between active and sham response rates. The re-estimation of sample size will be conducted by an independent biostatistician following a pre-specified plan as described by Mehta and Pocock, 2010 and presented to the independent data monitoring board (DMB).

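### Open-label response is calculated only in subjects observed at each visit, with no sensitivity analysis, so the Week 12 rate may be overstated if those who leave respond less often than those who stay

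*Protocol*

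**What the plan says.** Protocol 11.1 bases open-label summaries on the combined sTMS-treated population, "which consists of all subjects who have entered the six-week open label phase". It then narrows the data: "For the open-label phase, all efficacy analyses will be performed on the Observed Cases (OC) dataset only". The next sentence reads: "That is, no imputation for missing data will be used, and only data observed during the follow-up phase will be summarized".

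The SAP repeats the rule under General Overview of Methods: "All efficacy analyses will be performed on the Observed Cases (OC) dataset only for each week in this open-label Phase". Under Analysis of Primary Efficacy Endpoint it says that "the proportion of patients with a clinical response at each open-label visit for each double-blind treatment and for both treatments combined will be presented", and it calls these open-label analyses exploratory. Section H (Secondary Analyses for Label Considerations) compares the former arms at Week 12 on HAM-D17 change, MADRS change and MADRS response, again without imputation.

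Protocol 8.2 names lack of efficacy among the reasons for leaving. From subjects who discontinue, sites are to collect where possible at least the "primary reason for discontinuing, HAM-D, MADRS, current medication use, and adverse events".

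SAP Section F (multiple imputation and tipping point) concerns Week 6 only. SAP Section A tabulates discontinuation and its reasons only before Week 6; for the open-label phase it gives only the numbers entering. SAP Section L reports open-label exposure by week.

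**The concern.** The named population is all entrants, but the reported proportion describes only those still being assessed. A subject who starts open-label sTMS, sees no benefit and stops counts as a non-responder in the early weeks and is absent later. The exit HAM-D is sought, but no rule uses it at any later visit.

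If non-responders leave more often than responders, the weekly rate rises through attrition alone. Treatment is open and participation optional, so leaving for lack of benefit is a foreseeable route to missing data.

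At stake is the descriptive account of former sham subjects on active therapy and of non-remitters given up to 30 further sessions. A rate among stayers does not describe all those who started, and the planned tables would not show why the others left.

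**Working it through.** **Is there a figure to reproduce?** No. Neither document states an open-label sample size, dropout rate or response rate for this trial. What follows is algebra with assumed inputs.

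**Formula.** Let d be the share of entrants with no score at Week 12, pC the response rate among those observed, and pD the rate among those missing.

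- Observed-case rate = pC
- True all-entrant rate = (1 − d) × pC + d × pD
- Bias of the observed-case rate = d × (pC − pD)
- All-entrant rate with missing counted as non-response (pD = 0) = (1 − d) × pC

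**Inputs, all illustrative.** pC = 34% is borrowed from the sample-size assumption for active treatment, a double-blind per-protocol rate. For d, 0% and 10% are plain assumptions. The 23% comes from SAP Sample Size, which states that "approximately 23% of enrolled subjects may not be part of the PP population in each treatment group"; that is a double-blind share covering noncompliance as well as drop-out, not a rate of missing open-label scores.

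**Missing counted as non-response, pC = 34%:**

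| d | All-entrant rate | Gap, points |
|---|---|---|
| 0% | 0.34 × 1.00 = 34.0% | 0 |
| 10% | 0.34 × 0.90 = 30.6% | 3.4 |
| 23% | 0.34 × 0.77 = 26.2% | 7.8 |

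For observed-case rates from 20% to 50%, the gap is 2.0 to 5.0 points at 10% missing and 4.6 to 11.5 points at 23%.

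**Bias against the true all-entrant rate, pC = 34%:**

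| Leavers' response rate | d = 10% | d = 23% |
|---|---|---|
| None respond | +3.4 | +7.8 |
| Half the stayers' rate (17%) | +1.7 | +3.9 |
| Same as stayers (34%) | 0 | 0 |
| 1.25 times stayers' rate (42.5%) | −0.85 | −2.0 |

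The observed-case rate can never fall below the missing-as-non-response rate. Against the true rate, the sign depends on who leaves.

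**What the previous NEST trial suggests (Protocol 1.1).** The Completers set had 135 of the 202 ITT subjects, so 67/202 = 33.2% were outside it. HAM-D17 response was 27.2% (ITT) against 31.4% (Completers) on active, a gap of 4.2 points, and 27.3% against 27.7% on sham, a gap of 0.4 points. With pD = 0 and the pooled loss, the Completer rates would imply 31.4 × 0.668 = 21.0% and 27.7 × 0.668 = 18.5%, both well below the reported ITT rates. In treatment-naïve sham subjects, 18/37 responded in ITT and 15/25 among Completers, leaving 3 responders among 12 non-completers. So leavers did somewhat worse, but they were not all non-responders. These are double-blind data, and the protocol does not say how NEST handled missing scores.

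**Open-label retention in NEST.** Protocol 1.1 reports Week 10 assessments in 89 open-label participants and 31 non-entrants: 89 + 31 = 120, the whole per-protocol set. As written, that shows no loss at Week 10 in a selected cohort with a four-week open-label phase. It does not establish retention over six weeks here, but it is why the range for d must include zero.

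**The case against.** A reader might infer that the Week 12 rate is overstated as a matter of fact, by some 8 to 11 points: 34% falls to 26.2% at 23% missing and to 0.34 × 0.668 = 22.7% at NEST's 33.2%. The documents do not support that. Both loss figures are shares outside an analysis set, not shares without a score; a NEST non-completer could have a HAM-D yet fall short of 24 treatments within 60 days. Both come from the initial phase, whereas open-label entrants have already finished one treatment course. Zero response among leavers is the extreme case, and NEST's own gaps were 4.2 and 0.4 points. A responder who leaves early is dropped too.

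Three further objections have weight:

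- The consequence is limited. The open-label response analyses are labelled exploratory, the gatekept secondary outcomes are all at Week 6, and the phase has no concurrent control. Section H does not repeat the exploratory label for its Week 12 comparison, but that comparison is not in the testing sequence.
- Some non-responders have a reason to stay. Protocol 7.1 allows those not responding after three open-label weeks to be offered an added antidepressant, and they would then remain in the denominator.
- Part of the remedy can be rebuilt from planned output: entrants by arm, response counts, weekly exposure and full listings.

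What survives is narrower. The plan presents no rate for everyone who started, no sensitivity analysis for the open-label phase and no tabulated reasons for leaving it. A reader should not have to assemble these from listings.

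**Conclusion.** The point holds as a possible bias, not a demonstrated one. The Week 12 observed-case rate may be overstated; it will be if entrants who leave respond less often than those who stay. That direction is plausible, since lack of efficacy is a named reason for leaving, but the documents do not establish it for this phase.

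The size is unknown. At an assumed observed-case rate of 34%, the gap to the missing-as-non-response rate runs from 0 points with nobody missing to 3.4 points at 10% and 7.8 points at 23%. These gaps are the upper end of the bias at each level of missingness.

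The Week 6 primary analysis and its sample size are untouched, and the open-label response analyses remain exploratory. This is a worthwhile, inexpensive improvement in reporting, not a threat to the trial's main conclusion.

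**What to change.** Keep the observed-case rate and add the following in Protocol 11.1 and in the SAP (General Overview of Methods, Analysis of Primary Efficacy Endpoint, and Section H for Week 12 MADRS response):

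- At each open-label visit, report responders divided by all subjects who received at least one open-label session, with a missing score counted as non-response.
- Show the number entered and the number observed at each visit, by former double-blind arm and combined.
- Extend SAP Section A to tabulate open-label discontinuations by reason, using the information Protocol 8.2 already asks sites to collect.

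The cost is SAP wording, an extra row in the response tables and a short disposition table; no new visits, data or subjects are needed. The downside is that the all-entrant rate is pessimistic when subjects leave for reasons unrelated to effect, so both rates should stand side by side. The change addresses response rates only; the two continuous Week 12 endpoints in Section H would remain observed-case.
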